ANA – Antinuclear antibody
BAP – Biospecimens Accessioning and Processing
CACC – Colitis-associate colon cancer
CPN – Cancer Prevention Network
CRF – Case report form
CTL – Cytotoxic T-lymphocytes
DCP – NCI, Division of Cancer Prevention
dsRNA – double-stranded RNA
FAP – Familial adenomatous polyposis
FDA – Food and Drug Administration
HNPCC – Heritable nonpolyposis colorectal cancer
IBD – Irritable bowel disorder
IFNs – Interferons
IgG – Immunoglobulins
IND – Investigational new drug
IRB – Institutional Review Board
MDSC – Myeloid derived suppressor cells
MUC1 – Mucin 1 (high molecular weight type I transmembrane glycoprotein)
NCI – National Cancer Institute
NK – Natural killer cells
NF- κ B – Nuclear factor kappa-light-chain-enhancer of activated B cells
OAS – Oligoadenylate synthetase
PBMC – Peripheral blood mononuclear cells
PO – Participating Organization
Poly-ICLC – Polyinosinic-Polycytidylic acid stabilized with poly-L-lysine and carboxymethylcellulose (Hiltonol®)
PKR – Protein kinase receptor
SAE – Serious adverse events
T52 – Antibody titer at week 52
Th cells – T-helper cells
TLR – Toll like receptor
VNTR – Variable number of tandem repeats
WIWI – Was It Worth It Questionnaire

TABLE OF CONTENTS

Cover Page	1
Participating Institutions	2
Contacts	4
SCHEMA	5
Glossary	7

1. OBJECTIVES

1.1 Primary Objective

The primary objective of this trial is to compare the immunogenicity at week 12 of a MUC1 peptide vaccine with adjuvant (administered at 0, 2, and 10 weeks) in participants with a history of an advanced adenoma, randomized to receive MUC1 peptide vaccine versus placebo (Part I endpoint).

1.2 Secondary Objectives

Secondary objectives which correlate with the planned parts of the study include:

- To evaluate the ability of the vaccine to elicit a long-term memory response. We will administer a booster injection of the vaccine or placebo at week 53. Anti-MUC1 antibody response will be assessed at week 55 and compared to the week 52 pre-booster vaccine level (T55/T52). (Part II key secondary endpoint).
- To compare the adenoma recurrence rate from surveillance exams occurring at least 1 year and up to 3 years after Week 0 vaccine administration – MUC1 versus placebo (Part III key secondary endpoint).
- To compare the adenoma recurrence rates between MUC1 and placebo by excluding the following types of adenomas. These adenomas are excluded since they may represent missed or residual adenomas from the baseline exam. These analyses are exploratory.
 - Participants with adenomas ≤ 5 mm,
 - Participants with adenomatous tissue which may represent residual adenoma at the site of the previous advanced adenoma,
 - Participants with adenomatous tissue detected in the same segment of the bowel as the previous advanced adenoma.
- To assess adverse events to the MUC1 peptide vaccine in comparison to placebo during Parts I and II.
- To assess patient reported injection site reaction events from the Vaccine Report Card.

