7.5 Post-intervention Follow-up Period

For the purpose of monitoring adenoma recurrence and concomitant medications, contact by telephone will be made approximately every six months until Week 156 (Year 3) or the time of reported adenoma recurrence. Reports and specimens from any clinical colonoscopies will be obtained. Immune response will be tested. See Section 7.1 for details.

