8.2 Secondary and Translational Endpoints

The secondary endpoints will include the following:

- The Part I key secondary endpoint will be a comparison of the proportion of patients with at least a 2-fold increase in the IgG ratio between the 2 arms at 12 weeks.

- The Part II key secondary endpoint will assess the booster response at week 55 vs. week 52 for the vaccine as compared to placebo.
- The Part III key secondary endpoint will compare the adenoma recurrence rate from surveillance exams occurring at least one year and up to three years after Week 0 vaccine administration – MUC1 peptide versus placebo.

In addition to these key powered endpoints for the 3 different parts, we will also assess the following additional secondary endpoints:

- Comparison of adverse events between the MUC1 vaccine and placebo during Part 1 and 2.
- Comparison of the adenoma recurrence rates between MUC1 and placebo by excluding the following types of adenomas. These adenomas are excluded since they may represent missed or residual adenomas from the baseline exam. These analyses are exploratory.
 - Participants with adenomas ≤ 5 mm,
 - Participants with adenomatous tissue which may represent residual adenoma at the site of the previous advanced adenoma,
 - Participants with adenomatous tissue detected in the same segment of the bowel as the previous advanced adenoma.
- Assessment of participant-reported injection site reaction events from the Vaccine Report Card.

In addition, we will assess the following translational endpoints:

- To compare the anti-MUC1 antibody titer at the time of surveillance colonoscopy for the purpose of evaluating the anti-MUC1 antibody response in relation to adenoma recurrence. Since surveillance colonoscopy is generally at 3 years after an advanced adenoma, this titer will typically be obtained at approximately week 156.
- To evaluate MUC1 expression on baseline advanced adenomas and on recurrent adenomas detected at surveillance colonoscopy. Based on current knowledge of MUC1 expression and function in tumor cells, MUC1 negative adenomas are not expected to grow as immune escape variants, but this has never been tested before and the trial will provide an appropriate setting to study this issue.
- To evaluate levels of circulating myeloid derived suppressor cells (MDSC) in the vaccinated and the placebo group and correlate with anti-MUC1 antibody levels and adenoma recurrence (See Section 10.2.2).

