90 (45/arm)	40 vs. 15%	85%	0.05

4) As an exploratory analysis, we will also evaluate the adenoma recurrence rate from surveillance exams occurring at least 1 year and up to 3 years after Week 0 vaccine administration between MUC1 and placebo by excluding adenomas ≤ 5 mm, adenomatous tissue that may represent residual adenoma at the site of a previous adenoma, and adenomatous tissue detected in the same segment of the bowel as the previous advanced adenoma. These adenomas are excluded since they may represent missed or residual adenomas from the baseline exam. These analyses are exploratory.

5) Participant-reported injection site reaction information will be collected by use of a participant-completed Vaccine Report Card (Appendix E). Descriptive statistics will be used to summarize these data and compare the data between study arms.

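### The exploratory missed/residual-lesion analyses contradict themselves on whether lesions or participants are excluded, and give no denominator

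*Combined protocol and SAP*

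**What the plan says.** **Unit of exclusion.** Section 1.2 sets the objective "To compare the adenoma recurrence rates between MUC1 and placebo by excluding the following types of adenomas" and gives the reason: "These adenomas are excluded since they may represent missed or residual adenomas from the baseline exam". Both are about lesions. Each of the three bullets that follow begins with people. The third reads "Participants with adenomatous tissue detected in the same segment of the bowel as the previous advanced adenoma". Sections 8.2 and 13.1 repeat the lead-in, the reason and the bullets; the first bullet in 8.2 is "Participants with adenomas ≤ 5 mm". Section 13.5 item 4 describes the comparison as "between MUC1 and placebo by excluding adenomas ≤ 5 mm, adenomatous tissue that may represent residual adenoma at the site of a previous adenoma", and continues with same-segment tissue. It does not mention excluding participants.

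**Denominator.** Section 5.7.2 says who is evaluable for the Part III endpoint. No section says who is in the denominator of the exclusion analyses, or how a participant with both kinds of lesion is classified.

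**Status.** Section 13.5 item 4 states: "These analyses are exploratory". No power is claimed for them and no go/no-go rule uses them.

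**Follow-up.** Section 7.5 says "contact by telephone will be made approximately every six months until Week 156 (Year 3) or the time of reported adenoma recurrence", and then "Reports and specimens from any clinical colonoscopies will be obtained". The Part III schedule in 7.1 lists calls at weeks 88, 104 and 130 and a week 156 visit, with no stop at recurrence. Section 13.1 says that all patients are followed for the Part III endpoint.

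**The concern.** The stated reason for excluding something is that a particular lesion may have been there at baseline. That justifies not counting the lesion. It does not justify removing the person.

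Take a participant with a 4 mm adenoma and a separate 12 mm adenoma in another segment. Under the bullets this person leaves both numerator and denominator, although the 12 mm lesion is one the analysis has no reason to discount. Under 13.5 item 4 the person can stay and counts as a recurrence.

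Removal under the bullets depends on an outcome measured after randomisation that the vaccine is meant to change. The people left in each arm need not be comparable. Two analysts could follow different sections, obtain different results, and choose between them after seeing the data. These are the plan's only analyses directed at missed or residual lesions within its one clinical endpoint.

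The telephone rule in 7.5 bears on the same question. A lesion-level analysis needs to know about later exams in someone whose first adenoma was of an excluded type. Colonoscopy timing varies between people (7.1, footnote 12), and the calls are one way sites learn of it (7.1, footnote 10).

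**Working it through.** **The plan's own figures.** The plan states no figure for the exclusion analyses. The nearest is the Part III power table in 13.5 (45 per arm, one-sided alpha 0.05). A two-proportion test with pooled variance and no continuity correction gives 79.8%, 82.1% and 85.4% for 50 vs 25%, 45 vs 20% and 40 vs 15%, against the stated 79%, 82% and 85%. The sample follows from 110 × 0.9 × 0.9 = 89.1, about 90. So 45 per arm and a 45% placebo rate are used below.

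**Assumed inputs.** The documents give no frequency for any excluded lesion type, so every lesion mix here is an assumption. Write S for an excluded type and L for a counted type.

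- Lesion-level rate: P(L ≥ 1), over all evaluable participants.
- Participant-level rate: P(L ≥ 1 and S = 0) / P(S = 0).

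**Example 1: no effect on counted lesions.** Placebo: 25% S only, 10% L only, 10% both (45% in all). The vaccine removes every S and leaves L unchanged.

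- Lesion level: placebo 10% + 10% = 20%; vaccine 20%; difference 0.
- Participant level: placebo 10 / (100 − 25 − 10) = 10/65 = 15.4%; vaccine 20%; apparent harm of 4.6 points.
- The placebo denominator falls to 45 × 0.65, about 29.

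**Example 2: a real benefit, in counts per 45.** Placebo: 8 S only, 9 both, 3 L only (20/45). Vaccine: 3 S only, 1 both, 5 L only (9/45).

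- Lesion level: (9 + 3)/45 = 26.7% vs (1 + 5)/45 = 13.3%; vaccine better by 13.3 points.
- Participant level: 3/(45 − 17) = 3/28 = 10.7% vs 5/(45 − 4) = 5/41 = 12.2%; vaccine worse by 1.5 points.

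The sign reverses. In this mix S carriers fall from 17 to 4 and L carriers only from 12 to 6.

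**When bias arises.** Let lesion counts be Poisson with a shared gamma frailty of mean 1 and variance θ. For expected count m, P(no lesion) = (1 + θm)^(−1/θ). Set the placebo any-adenoma rate to 45%, with half of lesions of the excluded type.

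For θ = 1, 1/(1 + m) = 0.55 gives m = 0.818, or 0.409 per type.

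- Placebo: lesion level 1 − 1/1.409 = 29.0%; participant level 1 − 0.55/0.710 = 22.5%.
- Vaccine halving both types: lesion level 1 − 1/1.2045 = 17.0%; participant level 1 − 0.710/0.830 = 14.5%.
- Differences, taken before rounding: −12.1 and −8.0 points.

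| Scenario | Lesion level (points) | Participant level (points) |
|---|---|---|
| Types independent within arm | same rate | same rate |
| θ = 1, both types halved | −12.1 | −8.0 |
| θ = 2, both types halved | −11.5 | −4.9 |
| θ = 1, S cut 70%, L unchanged | 0.0 | +4.2 |
| θ = 2, S cut 70%, L cut 20% | −4.0 | +3.7 |
| θ = 1, S unchanged, L cut 70% | −18.1 | −14.5 |

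Independence gives no bias. Clustering with a proportional effect attenuates. In these scenarios, apparent harm or reversal appears only when there is clustering and the excluded types fall more than the others.

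**Loss of sample.** If 20% to 40% of participants carry an excluded lesion (assumed), participant exclusion leaves 45 × 0.8 = 36 down to 45 × 0.6 = 27 per arm.

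**Follow-up.** The number of later adenomas that might be missed under 7.5 cannot be computed from the documents.

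**The case against.** The lead-ins, the reason and the statistical section all speak of lesions, so a sensible analyst would probably exclude lesions and treat the bullets as loose drafting. The analyses are exploratory, unpowered and tied to no decision. Entry rules also guard against residual lesions: 4.1.1.2 requires presumptive evidence of complete removal, and 7.1 footnotes 4 and 5 defer enrolment until any early repeat exam is clear and require confirming reports. Randomisation should balance missed lesions in expectation. Example 1 is extreme, and its all-adenoma result would be 45% vs 20%, a favourable result on the key secondary endpoint.

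Most of this stands, and it limits the point. It does not remove it. The participant wording appears in all three bullets of three sections, and 13.5 item 4 does not settle the matter because it gives no denominator and no rule for people with both lesion types.

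A reader might infer from 7.5 that follow-up stops at the first adenoma. The documents do not support that. The clause limits telephone contact only. The next sentence obtains reports from any clinical colonoscopy, 7.1 keeps a week 156 visit that collects reports, 13.1 follows all patients, and 8.4 does not name recurrence as an off-study reason. Section 1.3 puts surveillance generally at 3 years, so a second exam inside the window may be uncommon. What remains is a risk that a later exam goes untracked, and passages to reconcile.

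**Conclusion.** The point holds as an unresolved contradiction in exploratory analyses. Lead-ins and 13.5 item 4 exclude adenomas, the bullets in 1.2, 8.2 and 13.1 exclude participants, and the denominator is missing. It should be corrected, because the literal bullets can give a wrong answer and the correction is cheap.

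A reader might go further and conclude that participant exclusion is the plan's settled rule, or that it will make an effective vaccine look harmful. Neither follows. The first ignores the lesion-level text beside the bullets. The second needs two conditions that the documents do not establish: clustering of lesion types within participants, and a larger vaccine effect on the excluded types. Clustering is plausible, since 6.8.2.7 and 13.2 stratify on the number of lesions, but it is not documented.

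Under the assumed mixes, the effect ranges from none (independence), through attenuation (12.1 to 8.0 points, or 11.5 to 4.9), to a reversed sign (−4.0 to +3.7 points). The primary endpoint and the key secondary endpoints are untouched by the exclusion wording.

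**What to change.** Use one lesion-level definition in 1.2, 8.2, 13.1 and 13.5 item 4. For each exclusion analysis:

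- the denominator is all participants evaluable for Part III (5.7.2), by arm;
- an event is at least one adenoma not of the excluded type, at exams from week 52 to week 156;
- a participant with only excluded lesions counts as having no event.

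Say whether the three exclusions are applied separately, together or both. Align the site wording too: 13.5 item 4 refers to any previous adenoma, and 1.2 to the previous advanced one.

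In 7.5, state that colonoscopy tracking and report collection continue to week 156 for everyone, including after an earlier adenoma, so that it agrees with 7.1 and 13.1.

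Make the change before recurrence is compared by arm. The cost is wording and at most the calls already scheduled at weeks 88, 104 and 130 for participants with an early adenoma. Section 10.2.3 shows that the Colonoscopy Report CRF numbers polyps individually. Its size and location fields are not shown, but either reading of the analysis needs them.

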1.3 Translational Objectives

- To compare the anti-MUC1 antibody titer at the time of surveillance colonoscopy for the purpose of evaluating the anti-MUC1 antibody response in relation to adenoma recurrence. Since surveillance colonoscopy is generally at 3 years after an advanced adenoma, this titer will typically be obtained at approximately week 156.
- To evaluate MUC1 expression on baseline advanced adenomas and on recurrent adenomas detected at surveillance colonoscopy. Based on current knowledge of MUC1 expression and function in tumor cells, MUC1 negative adenomas are not expected to grow as immune escape variants. This has never been tested before, and the trial will provide an appropriate setting to study this issue.
- To evaluate levels of circulating myeloid derived suppressor cells (MDSC) in the vaccinated and the placebo group and correlate with anti-MUC1 antibody levels and adenoma recurrence.
To establish a biospecimen repository archive including live cells, plasma, and germline DNA for future immunologic (e.g. MUC1-specific T cells) and other assays (systems biology approach to detect differences between responders and non-responders), testing not currently accommodated within the budget of this trial.

2. BACKGROUND

Randomized controlled trials demonstrate that endoscopic removal of adenomatous polyps reduces cancer incidence^{1,2}. However, there are many more adenomas than cancers, adenomatous polyp

recurrence rates are high, and repeated colonoscopic surveillance to monitor and remove recurrent adenomas is invasive, expensive, and associated with medical risk. Furthermore, surveillance colonoscopy is frequently misapplied, with excessive colonoscopy in low risk individuals and inadequate colonoscopy in some high risk individuals³. Immunotherapy targeting antigens known to be aberrantly expressed on colon cancers and polyps offers the potential for a relatively non-invasive and non-toxic prevention strategy, and because of the specificity of the immune response and its long-term memory, offers the potential for prolonged protection. Data suggest that aberrant expression of tumor antigens is subject to immune surveillance. During evolution from premalignant lesion to tumor, tumor-specific antibodies and T cells can be identified that in many animal models and human studies have been correlated with better prognosis. In a large study in colon cancer, that has now been repeated numerous times and in different types of tumors, infiltration of primary tumors with T cells was the best predictor of increased survival, surpassing even the cancer stage predictive value⁴. MUC1 vaccines to boost immune responses have been tested in colon cancer patients with advanced metastatic disease with a clinical response between 10% and 14%⁵. While the immune responses induced were by and large weak due to the generally immunosuppressed state of patients with advanced disease, in 22 studies that measured vaccine induced immune responses, humoral immunity was seen in 59% of patients and cellular immunity in 44%⁵. The limited effect of vaccine therapy in established cancer is now known to be due to numerous immunosuppressive mechanisms that develop in the cancer patient over time, caused either by the tumor or the immunotoxicity of standard cancer therapy, or both. Drugs, such as ipilimumab, are under development or being employed to modulate the tumor microenvironment to favor vaccine efficacy. However, most of these drugs are highly toxic in addition to being very expensive.

An opportunity to bypass these barriers is presented by the discovery that many of the tumor antigens in cancer vaccines are also expressed on precursor lesions, e.g. adenomatous polyps as precursors to colon cancer, PanINs to pancreatic cancer and CINs to cervical cancer, suggesting that immunization of patients with pre-malignant lesions before the tumor and cytotoxic therapy suppresses the immune response is possible and may be preferred. Our hypothesis is that a vaccine that elicits or boosts immune surveillance early in the oncogenic process will prevent malignant disease by eliminating premalignant lesions and preventing their recurrence and their progression to cancer. We are testing this hypothesis in the best elucidated pathway of premalignant to malignant progression, adenomatous polyp to colon cancer. The antigen we propose is MUC1, a tumor-associated antigen abnormally expressed on polyps and colon cancer^{6,7}, and the population for the planned intervention is individuals with advanced adenomas, a group at high risk for colorectal cancer, even years after initial diagnosis⁸.

MUC1: Mucins are large glycoproteins that consist of an extended polypeptide core that is heavily glycosylated by *O*-linked carbohydrates. Mucin 1 (MUC1) is a high molecular weight (>200,000 dalton) type I transmembrane glycoprotein. MUC1 is produced by cells of epithelial origin and expressed on the apical surface of these cells as they form glands. MUC1 is expressed by normal epithelial cells but in low levels, polarized to the apical surface, and with extensive glycosylation. MUC1 is a cell surface mucin that is able to induce a specific immune response^{9,10}. When cells undergo malignant transformation they produce hypoglycosylated MUC1 that has lost luminal polarity and is expressed at a much higher level than on normal cells. These characteristics allow its recognition by the immune system resulting in low-titer anti-MUC1 antibodies and MUC1 specific cytotoxic T-lymphocytes (CTL). Patients with adenocarcinomas of the breast, pancreas, and large bowel have T cells and antibodies that are directed to MUC1¹¹. The naturally occurring weak response is thought to be secondary to the lack of induction of MUC1 specific T-helper (Th) cells¹². A MUC1 vaccine that can boost that immune response, especially effector pathways that induce MUC1-specific Th cell responses, may be effective in controlling or

curtailing tumor growth. MUC1 is characterized by a large number of tandem repeats of 20 amino acids in the extracellular domain, which are quite immunogenic when underglycosylated, the form expressed on tumor cells^{13,14}. Recent work with T cells suggests that the immune response is directed to peptide and glycopeptide epitopes from the tandem repeat region exposed on the hypoglycosylated tumor form of MUC1. During neoplastic transformation, the amount of MUC1 produced by tumor cells increases and its glycosylation decreases thus increasing the number and density of epitopes that serve both as immunogens as well as targets of the immune response. The MUC1 molecule is also of interest because it binds β -catenin^{15,16} as well as intermediates in the *ras* signaling pathway¹⁷ promoting cell transformation. Thus, immunization against this molecule may affect premalignant cells in several different ways. Cytotoxic T cells generated by a MUC1 vaccine may directly destroy premalignant cells, while the antibodies may be involved not only in direct destruction of cells through antibody-dependent cell-mediated cytotoxicity (ADCC) or complement mediated lysis, but also by blocking signaling pathways that promote further neoplastic transformation.

Abnormal MUC1 expression has been a target for both active and passive immunotherapy of cancer in many pre-clinical and clinical studies¹⁸⁻²⁰. Targeting a molecule that is critical for cancer progression and survival lessens the chance that MUC1 negative mutant cancer cells would arise. In a recent NCI workshop on tumor antigen prioritization, MUC1 was ranked as the overall #2 priority target (only slightly behind WT1)²¹. Its priority was a result of 25 years of preclinical studies in animal models and almost 20 years of clinical trials, primarily in the therapeutic setting.

MUC1 vaccines: MUC1 proteins, peptides, glycopeptides or DNA-based vaccines have been widely used with or without adjuvants, loaded on DCs, with cytokines and immune stimulatory molecules, or engineered in various viral vectors, for treatment of cancer. These have been administered to patients with advanced disease and compromised immune systems. Even though the immune response induced by the vaccines was infrequent and at low levels, both humoral and cellular responses have been reported. In a meta-analysis published in 2006 of all clinical trials of MUC1 colon cancer vaccines published since 1985, consisting of 32 studies involving 527 colorectal cancer patients and accounting for 108 publications, utilizing MUC1 antigens that varied from whole tumors to individual peptides with a variety of adjuvants, toxicity was mild in the vast majority of studies, and manifest primarily as injection site symptomatology and flu like symptoms⁵. At the University of Pittsburgh Cancer Institute we have run seven clinical trials using the unglycosylated VNTR 100mer MUC1 peptide representing 5 tandem repeats, a highly immunogenic form not found on normal epithelial cells. Trials in resected pancreatic cancer were performed under the condition of minimal residual disease. In the first trial we used MUC1 100mer peptide plus the SB-A2 adjuvant from SKB²². The vaccine was safe and induced IgG and T cells responses in some patients. Two of 16 patients were alive and disease free at 32 and 61 months of follow up and no toxicity was seen that could be attributed to the vaccine. The second Part I/II trial used MUC1 100mer-peptide-loaded on DC. The vaccine was well-tolerated and non-toxic in 12 patients enrolled. The patients were followed for over four years and four of the twelve patients were alive without evidence of recurrence at 5 years.

Two decades of clinical trials targeting MUC1 in a variety of cancers in over 1200 patients were recently reviewed²³. Ongoing trials registered at clinicaltrials.gov identify an additional 2000 patients planned for anti-MUC1 therapy²³. The presence of anti MUC1 immunity in cancer patients favorably affects tumor development and prognosis²³.

MUC1 Peptide: Many types of vaccines have been tested by numerous investigators around the world incorporating a variety of MUC1 antigenic forms made immunogenic through the use of different adjuvants²³. Other forms, such as endogenously expressed MUC1 peptides via a plasmid, synthetic mRNA or a virus vector comprise only a minority of MUC1 vaccines. Synthetic MUC1 peptides have ranged from 16mer to 105mer in length and, with very few exceptions, they have all been derived from the VNTR tandem repeat sequence. The synthetic MUC1 tandem repeat peptides have been conjugated to immunogenic proteins or substrates, such as keyhole limpet haemocyanin (KLH) or mannan, mixed with various adjuvants such as Bacille de Calmette et Guërin (BCG), partially purified mycobacteria cell-wall skeleton and monophosphoryl lipid A (MPL) (DETOX), Quillaja Saponaria extract (QS-21), incomplete Freund's adjuvant (IFA) and QS-21 and MPL (SB-AS2). The 3-D structure of the MUC1 tandem repeat using 20, 40 and 60aa-long peptides has been characterized²⁴ and the optimal number of repeats for induction of immune responses or detection of antibodies in ELISA assays has been determined²⁵. The findings suggested that increasing numbers of tandem repeats elicited increasing titers of antibodies as well as detection levels of serum IgG in ELISAs. Attempts to synthesize long MUC1 peptides were successful first through manual synthesis and later also achieved through automatic synthesis. The optimal length was considered to correspond to 5 tandem repeats, 100aa, below which detection was weaker and above which no further benefit was seen. Thus the 100mer peptide became the vaccine antigen and the facility for production of the certified peptide for clinical use was established at the University of Pittsburgh.

Poly ICLC Adjuvant: Polyinosinic-Polycytidylic acid stabilized with poly-L-lysine and carboxymethylcellulose (Poly-ICLC, Hiltonol®) is a synthetic, non-replicating double-stranded ribonucleic acid (dsRNA), with no specific genetic message. It acts as viral-mimic with broad innate and adaptive immune enhancing, vaccine adjuvant, antiviral and antiproliferative effects^{25, 26}. These are mediated partly by its induction of a 'natural mix' of interferons (IFNs), cytokines, and chemokines, activation of natural killer [NK] cells, myeloid dendritic cells via TLR3 and MDA5, T4 and T8 cells, and activation of several nuclear and cytoplasmic enzyme systems (oligoadenylate synthetase [OAS], the dsRNA dependent protein kinase [PKR], RIG-I Helicase, and MDA5) that are involved in antiviral and antitumor host defenses. It has been shown to have broad gene regulatory actions as well. Poly-ICLC is currently being developed for the treatment of various disease indications in humans. Older studies in advanced cancer patients had shown a maximum tolerated dose of over 200 mcg/kg intravenously (IV), but Poly-ICLC has been administered intramuscularly (IM) 2 to 3 times weekly for years at doses of 10 to 50 µg/kg in patients with gliomas, multiple sclerosis or HIV/AIDS, and is well tolerated²⁷⁻²⁹. Three recent phase II multicenter trials of Poly-ICLC 20 mcg/kg IM 3 times weekly in over 180 patients with gliomas have confirmed safety and potential efficacy (see poly ICLC investigational brochure). Poly-ICLC is also being used for various cancer vaccine platforms in about two dozen, ongoing phase I/II clinical trials in patients with glioma, hepatoma, lymphoma, prostate, cervical, ovarian, breast, colon, and pancreatic cancers.

About 400 patients have been safely treated in those trials to date (see poly ICLC investigational brochure). The most common side effects of low-dose Poly-ICLC are temporary discomfort at the injection site and occasional transient malaise that lasts for several hours. Occasionally, patients on low-dose Poly-ICLC have developed a flu-like syndrome with fever, chills, and malaise. This syndrome typically resolves in 12 to 24 hours, responds to acetaminophen, and does not recur on subsequent dosing. Subcutaneous dosing, especially with vaccine, can also result in transient injection site erythema. Poly-ICLC has also been used nasally in a recent phase I randomized dose escalation trial in humans (N=50), and was well tolerated.

Vaccines for Prevention

Other than viral vaccines for cancers of known viral origin, vaccines for prevention of cancer have not received sufficient attention. Yet, there are many non-viral antigens that are differentially expressed between normal and cancer cells, such as MUC1, that are perceived by the immune system as foreign and to which immune responses can be safely generated through vaccination. In preclinical animal models of human cancer, these vaccine-elicited immune responses have prevented cancer development or cancer progression. These studies have served as the basis for the first clinical feasibility study of the MUC1 peptide vaccine in individuals with the history of advanced adenoma who are considered at increased risk for developing colon cancer³⁴. This study showed that the vaccine consisting of 100mcg of the synthetic 100mer MUC1 peptide admixed with the TLR-3 agonist Hiltonol as adjuvant, induced anti-MUC1 IgG and long term immune memory thus confirming its immunogenicity. The study also showed that individuals with above normal numbers of circulating myeloid derived suppressor cells (MDSC) were prevented from responding to the vaccine. The randomized placebo-controlled trial described in this protocol will confirm the vaccine immunogenicity and its dependence on the MDSC and compare adenoma recurrence in vaccine responders vs. non-responders.

Colorectal Adenomas

MUC1 is overexpressed and hypoglycosylated on premalignant lesions such as adenomatous polyps, and its expression is significantly greater with higher degrees of dysplasia⁷. MUC1 is functionally important in the maintenance of the malignant phenotype. Thus, induction of an immune response against MUC1 in the setting of pre-malignancy, such as in patients with adenomatous polyps, may protect from polyp recurrence as well as from progression to cancer.

[figure not shown]

Figure1: Abnormal MUC1 is overexpressed and hypoglycosylated. Hypoglycosylated MUC1 exposes the disaccharide T antigen and the shorter monosaccharide Tn antigen attached to the protein backbone of MUC1 molecules.

Mouse model of MUC1 vaccine for colon cancer prevention

Mouse experiments have been performed over the years to test the immunogenicity, safety and efficacy of MUC1 vaccines. One of the best mouse models has been the MUC1 transgenic mouse that expresses human MUC1 under its own promoter and thus maintains tissue specific expression, including undergoing changes in expression during tumorigenesis. Most vaccines tested in human clinical trials showed both high immunogenicity and high efficacy in mouse models. It should be emphasized that this result was always achievable in the prevention setting and worked in the therapeutic setting only when the tumors were extremely small (e.g. 3-day tumors). Vaccination in the setting of a larger or metastatic tumor was never successful. Experiments in spontaneous mouse tumor models, though more labor intensive and of longer duration, are a good reflection of the immunosurveillance of the emerging tumor by the immune system and more closely resemble human disease than transplantable tumor models. A well-known model of human colon carcinogenesis is the Apc/MIN mouse that develops spontaneous adenomatous polyps that can develop into cancer. This mouse was crossed to the MUC1 transgenic mouse and both the polyps and the resulting tumors expressed the abnormal MUC1 and could be

targeted by a MUC1 vaccine. In the MIN mouse, a MUC1-based vaccine caused flattening of adenomas and significantly reduced the number of large adenomas³⁵. Immunization was successful in generating a MUC1-specific immune response.

Two recent MUC1 vaccine studies in mouse tumor models of colorectal cancer were recently performed. In an IL-10^{-/-} mice that spontaneously develop inflammatory bowel disease (IBD) and progress to colitis associated colon cancer (CACC), crossed with MUC1 transgenic mice, a MUC1 vaccine that induced humoral and cellular anti-MUC1 immunity reduced inflammation and prevented development of CACC³⁶. The same result was obtained in a dextran sodium sulfate (DSS) model of CACC where the MUC1 vaccine reduced chronic colitis, prevented development of dysplasia, and extended survival³⁷. While this is a different route of colon cancer development in that these are inflammatory models, the model shows both efficacy and safety of the vaccine-induced anti-MUC1 immunity.

